3.2 Exclusion Criteria

Participants who exhibit any of the following conditions at screening will not be eligible for admission into the study.

- 3.2.1 First diagnosis of prostate cancer > 12 months prior to enrollment
- 3.2.2 Prior prostate cancer-directed therapy including:
 - 3.2.2.1 androgen deprivation therapy
 - 3.2.2.2 radiation therapy to the prostate (external beam or brachytherapy)
 - 3.2.2.3 cryotherapy
 - 3.2.2.4 high-intensity focused ultrasound (HIFU)
 - 3.2.2.5 chemotherapy for prostate cancer
- 3.2.3 Prior transurethral resection of prostate
- 3.2.4 Subject who is deemed by the treating physician to have a contraindication to definitive treatment
- 3.2.5 Subjects with a contraindication to an MRI including those with a pacemaker, ferromagnetic aneurysm clip, or cochlear implants
- 3.2.6 Subjects with a contraindication to receiving Gadolinium containing contrast for the MRI
- 3.2.7 Conditions which make repeat TRUS biopsies not feasible

3.3 Inclusion of Women, Minorities and Other Underrepresented Populations

The only patient population which is excluded from this study is women by virtue of the fact women do not get prostate cancer. All other populations are potentially eligible for enrolment

Accrual Targets						
Ethnic Category	Sex/Gender					
	Females		Males		Total	
Hispanic or Latino	0	+	10	=	10	
Not Hispanic or Latino	0	+	120	=	120	
Ethnic Category: Total of all subjects	0	+	130	=	130	
Racial Category						
American Indian or Alaskan Native	0	+	0	=	0	
Asian	0	+	8	=	8	
Black or African American	0	+	8	=	8	
Native Hawaiian or other Pacific Islander	0	+	0	=	0	
White	0	+	114	=	114	
Racial Category: Total of all subjects	0	+	130	=	130	

4. REGISTRATION PROCEDURES

4.1 General Guidelines for DF/HCC and DF/PCC Institutions

Institutions will register eligible participants with the DF/HCC Quality Assurance Office for Clinical Trials (QACT) central registration system. Registration must occur prior to the initiation of therapy. Any participant not registered to the protocol before treatment begins will be considered ineligible and registration will be denied.

A member of the study team will confirm eligibility criteria and complete the protocol-specific eligibility checklist.

Following registration, participants may begin protocol treatment. Issues that would cause treatment delays should be discussed with the Principal Investigator. If a participant does not receive protocol therapy following registration, the participant's protocol status must be changed. Notify the QACT Registrar of participant status changes as soon as possible.

4.2 Registration Process for DF/HCC and DF/PCC Institutions

The QACT registration staff is accessible on Monday through Friday, from 8:00 AM to 5:00 PM Eastern Standard Time. In emergency situations when a participant must begin treatment during off-hours or holidays, call the QACT registration line at and follow the instructions for registering participants after hours.

The registration procedures are as follows:

- 1. Obtain written informed consent from the participant prior to the performance of any study related procedures or assessments.
- Complete the protocol-specific eligibility checklist using the eligibility assessment documented
 in the participant's medical/research record. To be eligible for registration to the study, the
 participant must meet each inclusion and exclusion criteria listed on the eligibility
 checklist.

Reminder: Confirm eligibility for ancillary studies at the same time as eligibility for the treatment study. Registration to both treatment and ancillary studies will not be completed if eligibility requirements are not met for all studies.

- 3. Fax the eligibility checklist(s) and all pages of the consent form(s) to the QACT.
- 4. The QACT Registrar will (a) validate eligibility, (b) register the participant on the study, and (c) randomize the participant when applicable.

5. The QACT Registrar will send an email confirmation of the registration and/or randomization to the person initiating the registration immediately following the registration and/or randomization.

4.3 General Guidelines for Other Participating Institutions

N/A

4.4 Registration Process for Other Participating Institutions

N/A

5. TREATMENT PLAN

This is a single arm, prospective protocol investigating the sensitivity and specificity of MP-erMRI in assessing disease extent and grade relative to initial re-biopsy in men with low-risk prostate cancer who select AS as their initial treatment strategy. Following enrollment and registration, subjects will complete baseline patient-reported health state questionnaires.

Between 2 and 14 months following initial diagnostic biopsy, they will undergo a MP-erMRI. This will be systematically reviewed and men will be characterized into three groups: (1) "not reclassified" characterized by findings consistent with small, low-Gleason grade organ-confined tumors, (2) "reclassified" characterized by large, higher-Gleason grade organ-confined tumors, and (3) radiographic T3 and/or N1 disease. Those in group 3 will come off of protocol and proceed to management as per their treating physician. Those in groups 1 and 2 will proceed within 3 months of the MRI to a standard 12-core TRUS biopsy. For those in group 2 at the time of TRUS biopsy, they will also have a for-cause targeted biopsy of the lesion seen on MP-MRI. All men in groups 1 and 2 who do not have their disease reclassified with the TRUS biopsy or for-cause biopsy will proceed with AS as per their treating physician. Those who are pathologically reclassified will be managed per their treating physician. All study participants will come off study after the end of study visit that occurs within 60 days following the final biopsy.

Information about participants will be gathered according to the study calendar.

5.1 Patient-reported health states

Participants will be asked to complete patient-reported health state questionnaires at enrollment and following the final on-protocol biopsy. The questionnaire that will be provided to participants for self-administration will include the following:

- The Mishel Uncertainty in Illness Scale Community Form for Active Surveillance (MUIS-AS, Appendix A). The MUIS-AS will evaluate uncertainty, anxiety, and distress associated with the patient's cancer diagnosis.
- *The Service Satisfaction Scale for Cancer Care* (SSS-Ca, Appendix B). The SSS-Ca will evaluate the patient's satisfaction with both the process and outcome of their cancer related care.
- The Expanded Prostate Cancer Index Composite Clinical Practice (EPIC-CP, Appendix C). The EPIC-CP is used to evaluate urinary and sexual function following treatment for prostate cancer. This will specifically be useful in order to assess the progression of urinary symptoms

- overtime in these participants who may be required to undergo serial prostate biopsies, endorectal MRI, etc.
- The American Urological Association Symptom Index (AUA SI, Appendix D), which will be used to evaluate overall urinary bother and function

Questionnaires will be given to participants at their enrollment visit and at the end of study visit following biopsy. Participants will be instructed to complete them independently and to return them by mail to the project coordinator.

5.2 Multiparametric MRI

Between 2-14 months following the initial diagnostic biopsy, participants will undergo an endorectal prostate MRI. A 2-month delay from the initial biopsy is preferred to minimize the effects of post-biopsy hemorrhage. All MR examinations will be performed on a 3T whole-body scanner possessing a whole-body gradient coil set with sufficient strength and speed to perform an optimized MP-MRI, a whole body transmit/receive coil, an external rigid phased-array torso coil, and an MR-compatible power injector for administering intravenous contrast. A compatible endorectal coil will be used for phased-array/ecoil measurements. All studies will be obtained with the image plane perpendicular to the rectal wall/prostate interface.

5.2.1 Protocol:

5.2.1.1 The standardized 3T pulse sequences we will use will include fast spin echo (FSE) for T2 weighted-images (FOV: 14-18cm; slice thickness: 3mm; spacing: 3mm; TR/TE: 3000/102 msec; Matrix: 384x256; NEX=3). Dynamic Contrast Enhanced (DCE) imaging will be performed with 3D-Fast spoiled gradient (FSPGR) images using FOV: 26 cm; slice thickness: 6mm; spacing: 6mm; Matrix: 256x160; contrast (Gadolinium gadopentetate (Gd)) injection rate of 3mL/sec; slab thickness 16-20 slices, 5 sec/volume, repeat 60 times, with a total scan time of 5 minutes. Pharmacokinetic analyses of each slice will be performed using a custom research tool (OncoQuant, GE Global Research) using a population averaged bi-exponential arterial input function augmented with a first pass peak[69]. Single shot echo planar diffusion weighted imaging (DWI) will be performed using b values of 0 and 500, and 0 and 1400 with trace ADC maps generated at all b values.

5.2.2 Image Interpretation:

5.2.2.1 Images will be reviewed within the radiology department where the scans were obtained as per current protocols and a standard clinical report will be produced. Images will subsequently be analyzed by study radiologists with extensive experience in GU imaging. The images will be evaluated according to the proposed PIRADS scoring system guidelines. This will specifically look at signal intensity on T2 weighted image (with a discrete, homogenous low signal focus being suspicious for tumor). For DCE, both semi-quantitative and quantitative parameters will be evaluated, with particular attention paid to the dynamic enhancement curve type [70]: (type 1, persistent increase; type 2, plateau; and type 3, decline after initial upslope; type 3 being considered the most suspicious for

prostate cancer, particularly in the presence of a focal asymmetric enhancing lesion). Pharmacokinetic modeling, which will produce quantitative indices [such as K^{trans} (forward volume transfer constant) and v_e (fractional extracellular space)], will be incorporated into the analysis. DWI will also be scored according to signal intensity on high b value image (\geq b1000) and values obtained on ADC map. Index lesion size will be measured on T2WI to categorize those \geq or< 1 cm in size. Extracapsular extension (ECE) and seminal vesicle invasion (SVI) will also be evaluated for.

The interpretation of the MRI will place participants into the following categories:

- 1. **Not-reclassified**: any identified abnormality of the MRI is confined to the gland without definitive evidence of ECE or SVI. Additionally, no lesion is greater than 1 cm in size nor do any identifiable lesions have characteristics of high Gleason grade.
- 2. **Reclassified**: Disease appears to be confined to the prostate (no ECE or SVI) but one or more lesions appear either >1 cm in size or have imaging characteristics concerning for higher Gleason grade disease.
- 3. **T3 or N1:** disease appears to be clearly extending outside the prostate and/or into the seminal vesicles or there is evidence of pathologic involvement of lymph nodes.

If the MRI places a subject into the T3/N1 category, they will meet criteria for coming off protocol and will then receive further treatment per their treating physician. If a participant is in either the **not-reclassified** or the **reclassified** categories, they will proceed with the planned biopsy.

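### Do the lesion-size and ECE/SVI wordings in section 5.2.2 leave the MRI axis of the primary 2x2 table undefined?

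*Combined protocol and SAP*

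**What the plan says.** Section 5.2.2 contains two statements about size. The first is a measurement: "Index lesion size will be measured on T2WI to categorize those" at or above 1 cm versus below it. The second is the classification. In group 1 (not reclassified), "no lesion is greater than 1 cm in size nor do any identifiable lesions have characteristics of high Gleason grade". In group 2 (reclassified), "one or more lesions appear either >1 cm in size or have imaging characteristics concerning for higher Gleason grade disease".

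On extracapsular extension (ECE) and seminal vesicle invasion (SVI) the three groups use three wordings:

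- Group 1: "any identified abnormality of the MRI is confined to the gland without definitive evidence of ECE or SVI".
- Group 2: "Disease appears to be confined to the prostate (no ECE or SVI", with the parenthesis closing there.
- Group 3: "disease appears to be clearly extending outside the prostate and/or into the seminal vesicles", or involved lymph nodes.

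The consequence of group 3 is stated once and plainly: "If the MRI places a subject into the T3/N1 category, they will meet criteria for coming off protocol". Under section 5, men in groups 1 and 2 go on to a 12-core TRUS biopsy, and for group 2 "they will also have a for-cause targeted biopsy of the lesion seen on MP-MRI". Section 11.4 calls the study positive if the lower limit for the true positive fraction (TPF) exceeds 70% and the upper limit for the false positive fraction (FPF) is below 20%, using 90% intervals.

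**The concern.** The MRI group is the index test, so an unclear group boundary is an unclear test result.

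On size, a lesion of exactly 1.0 cm sits in the upper recorded bin but, on size alone, in the MRI-negative group. An analyst who rebuilt the groups from the bin would get a different table. The bin also covers only the index lesion, whereas the groups look at any lesion.

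On ECE/SVI, take a man without nodal disease whose extension is suspected but not clear, and who has a lesion above 1 cm or high-grade features. He fails group 1 on size or grade, group 2 on its parenthesis and group 3 on the word requiring clarity. If one reader put him in group 2 and another in group 3, the choice would decide whether he is in the table at all. Such men are not a neutral subset. In the immediate-rebiopsy series described in section 2.1, 39% of men with concerning MRI features were upstaged or upgraded, against none of those without evidence of ECE.

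**Working it through.** **Step 1: the plan's own figure.** Inputs from sections 11.2 and 11.3: 30 upgraded and 90 not upgraded men, TPF 90%, FPF 6%. With exact (Clopper-Pearson) 90% limits, the success rule needs at least 26/30 true positives and at most 11/90 false positives.

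- P(X ≥ 26 | n = 30, p = 0.90) = 0.8245
- P(Y ≤ 11 | n = 90, p = 0.06) = 0.9925
- Product = 0.818, against the stated 81%.

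The same limits are therefore used below. The wording question does not touch the sample size.

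**Step 2: enumerate the definitions.** For men without nodal disease, cross ECE/SVI (none, equivocal, clear) with largest lesion (<1, =1, >1 cm) and high-grade features (no, yes). This gives 3 × 3 × 2 = 18 combinations.

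| ECE/SVI | No lesion >1 cm, no high-grade features | Lesion >1 cm or high-grade features |
|---|---|---|
| None | Group 1 (2 combinations) | Group 2 (4) |
| Equivocal | Group 1 (2) | No group, literally (4) |
| Clear | Group 3 (2) | Group 3 (4) |

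Fourteen combinations fit exactly one group, four fit none, and none fits two. Every combination with a lesion of exactly 1 cm and no high-grade features has a single group.

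**Step 3: can the text resolve the four cells?** Group 3 needs clear extension or nodes, so an equivocal finding is not group 3. Sections 5 and 5.2.2 take men off protocol on MRI only for group 3. Section 5.3 gives a TRUS biopsy to everyone still on protocol after the MRI. Section 2.2 says that men whose scans suggest more extensive or higher-grade disease are biopsied. The man therefore stays on protocol and is biopsied. Size or grade rules out group 1, so group 2 is what remains. This is a reading of the text, not a view on how such men should be managed.

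**Step 4: how much would a wrong reading move the result?** The starting point is the planned 27/30 (lower limit 76.1%) and 5/90 (upper limit 11.3%).

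*Size.* Using the bin in place of the group definitions can move men only one way, from MRI-negative to MRI-positive.

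- One true positive gained: 28/30, lower limit 80.5%, pass.
- Six false positives gained: 11/90, upper limit 19.4%, pass.
- Seven gained: 12/90, upper limit 20.7%, fail.

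Seven of the 85 planned true negatives is 7/85 = 8.2%. All seven would need a largest lesion of exactly 1.0 cm.

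*ECE/SVI, men wrongly removed.* Six true positives leaving gives 21/24, lower limit 70.8%, pass. Seven gives 20/23, 69.6%, fail.

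*ECE/SVI, men added.* Suppose all of the roughly 10 men that section 11.1 expects in group 3 were read as group 2, with 39% upgraded (assumption, from the series in section 2.1). That is 4 upgraded and 6 not.

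- TPF (27 + 4)/(30 + 4) = 31/34, lower limit 78.7%, pass.
- FPF (5 + 6)/(90 + 6) = 11/96, upper limit 18.3%, pass.
- Seven added men not upgraded: 12/97, 19.3%, pass. Eight: 13/98, 20.3%, fail.

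**The case for a change.** The strongest case for a change is that a diagnostic study should define its positive test so that a second reader can reproduce it, and that rewording costs almost nothing. The TPF margin is also thin. If true positives were moved to MRI-negative, losing one gives 26/30 (72.0%, pass) but losing two gives 25/30 (68.1%, fail). The arithmetic stands. However, the group definitions already place the 1.0 cm lesion in group 1, and using the bin instead moves men the other way. The two-man loss arises only if the planned counts are taken to have been set by the bin, and nothing in the plan says so.

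A second argument is that equivocal ECE could be common. In the rebiopsy series, 27% of scanned men had a finding concerning for ECE, while section 11.1 expects under 10% in group 3. Applied to 130 men, that is 0.27 × 130 ≈ 35 against 10, or about 25 men, and an analysis set of about 95 rather than 120. This bound does not stand. It needs men to be removed without clear extension, contrary to the text, and it needs every one of them to have a large or high-grade lesion. The subset is also a poor basis for scaling. About 0.64 × 104 ≈ 67 men were scanned, 0.27 × 67 ≈ 18 had concern for ECE, and 0.39 × 18 ≈ 7 were upgraded, which is about 10.5% of those scanned. The whole series had 27%, about 28 men, so the unscanned men must have run at about (28 − 7)/(104 − 67) = 57%.

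A lesser point is that section 11 does not cite section 5.3.4.2 as its definition of disease upgrade, and that the lead-in there refers to eligibility criteria, which in section 3.1 also cover tertiary grade and ECE on biopsy. The list itself gives three explicit TRUS thresholds that match the extent-or-grade objective, so an analyst would use them.

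What remains is that the parenthesis in group 2 is looser than the wording around it, and that one comparison sign differs from the other two.

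**Conclusion.** The inconsistencies are genuine but clerical. The two definitions that build the table agree on size, and the rules for leaving the protocol and for biopsy place the unassigned man in group 2 by elimination. An analyst following the group definitions gets a sound 2x2 table, and the stated 81% power is unaffected.

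The documents give no frequency for either kind of man, so the counts above are break-even figures and not estimates. Seven extra false positives would be needed for the size slip to reverse a planned positive result, and seven lost true positives or eight added false positives for the ECE/SVI slip. The conclusion assumes that men are classified by the group definitions and not by the recorded index-lesion bin, and that men leave the protocol on MRI only for clear extension or nodal disease, as the text says. Reconciling the wordings would be tidy and is for the study team, but the analysis does not depend on it.

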5.3 Prostate biopsy

All subjects who remain on protocol following the MP-MRI will undergo an on-protocol TRUS biopsy within 3 months of the MRI. This biopsy will therefore take place between approximately 2-17 months following their initial diagnostic biopsy.

5.3.1 Prophylaxis

5.3.1.1 Participants will be recommended to receive oral or IV antibiotic prophylaxis according the American Urologic Association Guidelines (http://www.auanet.org/content/media/antimicroprop08.pdf) and as per the standard of the institution. Further, anticoagulant or antiplatelet directed therapy will be managed prior to biopsy as per the standard of the participating institution.

5.3.2 TRUS Biopsy Sampling

A 12-core biopsy will be performed without specific targeting of lesions noted at the time of MRI. This approach is intended to provide an unbiased assessment of the accuracy of MP-MRI in predicting men reclassified based on the current gold standard TRUS rebiopsy. Each core will be individually labeled with laterally and anatomic site within the prostate.

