5.3.3 Targeted rebiopsy

Participants in the **reclassified** category will have both a 12-core TRUS biopsy unguided by the results of the MRI and a biopsy targeting the lesion(s) of concern from the scan. The rationale for doing both biopsies is that to compare the MRI findings to the current goldstandard, a non-targeted TRUS biopsy, we need to include this regardless of the MRI findings. Because this biopsy may not capture the lesion noted on the scan, a targeted biopsy will be performed at the same time. The targeted biopsy will be performed according to the practices of the treating institution but will generally consist of conscious sedation with either an MRI-guided biopsy or a TRUS-guided biopsy directed based on images fused to the MRI. The number of cores taken will be at the discretion of the physician performing the biopsy. Standard of care transrectal ultrasound imaging (TRUS) may be augmented with the setup needed for spatial tracking of the TRUS images. The purpose of this is to facilitate research in spatial mapping biopsy samples within the prostate gland, and to aid with correlation of pathology analysis of the samples with TRUS and MRI imaging data. The tracking setup would be enabled by a tracking system consisting of an electromagnetic field transmitter that establishes the coordinate frame for tracking volume, and several sensors. The transmitter would be mounted on an articulated arm to the patient bed. One sensor will be attached to the handle of the TRUS probe before the procedure. The sensor will remain on the handle outside the patient at all times. The second sensor will be attached with the medical tape to the back of the patient. Prior to TRUS imaging, a calibration procedure may be necessary. If needed, such procedure would involve placing the TRUS probe in a water bath and imaging of a phantom, prior to the patient procedure. This component of the biopsy is not anticipated to add any additional risk or toxicity to the protocol.

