5.3.4 Pathologic assessment

- 5.3.4.1 All specimens will be formalin fixed and paraffin embedded as per usual clinical care. Pathology will be reviewed by a pathologist with GU expertise for Gleason grade, disease extent, and number of cores positive. Additional features such as perineural invasion and high-grade PIN will be noted though these will not be used to determine continued protocol eligibility. Each of the cores will be labeled for biopsy location at the time of procedure and will be individually reported. Pathology will be reviewed at the treating center. Specimens will also be labeled as to whether they came from the TRUS biopsy or the targeted biopsy
- 5.3.4.2 TRUS Biopsy: Participants will come off study if they no longer meet eligibility criteria following rebiopsy:
 - >3 cores positive for cancer
 - >50% of any single core containing cancer
 - any Gleason >3+3

- 5.3.4.3 Targeted Biopsy: Participants will be considered pathologically reclassified if either of the following criteria are met on the targeted biopsy:
 - Gleason >3+3
 - >7mm of any core involved with cancer

In this situation, using the criteria of number of cores involved with cancer will no longer be comparable across participants as the number of cores sampled will be variable based on the situation.

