7. STUDY CALENDAR

	Pre- Study	MRI Visit (2-14 months post initial biopsy)	Final Bx visit (within 3 months of MRI visit)	End of Study Visit (within 60 days of final bx)
Informed consent	X			
History ^a	X			
Pathology review	X ^b		X ^d	
PSA	X ^c			Xe
Concurrent meds	X			
Height and weight	X			
Performance Status	X			
Patient-reported health	X^{f}			X
Adverse event evaluation		X	X	X

- a: biopsy date, clinical T-category, was the subject staged with a CT of the abdomen and pelvis; was the subject staged with a bone scan; ACE-27 Comorbidity index (Appendix E)
- b: DF/HCC pathology review of original biopsy (no. cores taken, no. cores positive for cancer; % involvement for each positive core; Gleason grade for each positive core; presence and grade of tertiary Gleason grade; evidence of extracapsular extension; evidence of perineural invasion)
- c: last PSA level prior to biopsy diagnosing the prostate cancer
- d: DF/HCC pathology review of "random" and targeted biopsy (as needed) (no. cores taken, no. cores positive for cancer; % involvement for each positive core; Gleason grade for each positive core; presence and grade of tertiary Gleason grade; evidence of extracapsular extension; evidence of perineural invasion)
- e: most recent PSA value
- f: MUIS-AS, Appendix A; SSS-Ca, Appendix B; EPIC-CP, Appendix C; AUA SI, Appendix D

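### Nothing masks the operator or pathologist to the MRI or sets the core order, so in MRI-positive men the reference biopsy is open to influence from the test it judges

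*Combined protocol and SAP*

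**What the plan says.** Section 11.2 makes the TRUS re-biopsy the gold standard, so the 12-core result decides which men count toward TPF and which toward FPF. Section 5.3.2 requires that "A 12-core biopsy will be performed without specific targeting of lesions noted at the time of MRI" and gives an unbiased assessment of the MRI as the aim. Section 5.3.3 repeats the point for men in the reclassified category, who have a "12-core TRUS biopsy unguided by the results of the MRI". For these men "a targeted biopsy will be performed at the same time", by "either an MRI-guided biopsy or a TRUS-guided biopsy directed based on images fused to the MRI" according to local practice. Sections 2.2 and 5 also place both biopsies in one session. None of these sections gives an order.

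On pathology, section 5.3.4 requires a pathologist with genitourinary expertise and individual reporting of cores, and adds: "Specimens will also be labeled as to whether they came from the TRUS biopsy or the targeted biopsy". Note d of the Study Calendar has one review item that covers the random biopsy "and targeted biopsy (as needed"). Section 5.2.2 has a standard clinical MRI report produced for each scan. No section withholds that report, or the MRI category, from the person taking the 12 cores or the person reading them.

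**The concern.** An instruction not to target is neither masking nor sequencing. In group 2 the operator may have the lesion on screen, or may already have sampled it, when the 12 template cores are taken. The plan would hold no record of this. The pathologist needs no MRI report: targeted cores exist only in men with a positive MRI, so a case containing them reveals the index-test result.

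Influence on the 12-core result in MRI-positive men would move both co-primary measures at once. If it runs toward the MRI (a template core strays to the lesion, or a borderline core is read up), false positives become true positives: TPF rises and FPF falls. If it runs away from the MRI (template cores avoid a lesion left to the targeted cores), true positives become false positives: TPF falls and FPF rises. With only about 30 upgraded men expected, a few changed results matter.

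**Working it through.** **Inputs.** Sections 11.2 and 11.3: 120 evaluable men, 30 upgraded and 90 not; promising values TPF 90%, FPF 6%; unacceptable values TPF 70% or below, FPF 20% or above; one-sided alpha 0.1; power 81%. Section 11.4: a positive conclusion needs the lower limit of TPF above 70% and the upper limit of FPF below 20%. That section states 90% intervals but tabulates 80% intervals, so both are carried through. The drift rate q, the share of affected MRI-positive men whose 12-core result changes, is an assumption; the documents give none.

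**Reproducing the plan's power.** With exact (Clopper-Pearson) 90% limits, success needs at least 26 of 30 true positives and at most 11 of 90 false positives. Power at 90/6 is 0.8245 × 0.9925 = 0.818, close to the stated 81%. With 80% limits the cut-offs are 25 and 12, and power is 0.9268 × 0.9972 = 0.924.

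**Model.** TP ~ Bin(30, TPF) and FP ~ Bin(90, FPF). Conversions ~ Bin(FP, q) for drift toward the MRI, or Bin(TP, q) for drift away. Converted men change both numerators and both denominators, the limits are recomputed, and the joint rule is applied by exact enumeration.

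**Expected apparent values.**
- Toward the MRI, true 90/20: TPF = (27 + 18q)/(30 + 18q), FPF = 18(1 − q)/(90 − 18q). At q = 0.10: 28.8/31.8 = 90.6% and 16.2/88.2 = 18.4%.
- Away from the MRI, true 90/6: TPF = 27(1 − q)/(30 − 27q), FPF = (5.4 + 27q)/(90 + 27q). At q = 0.10: 24.3/27.3 = 89.0% and 8.1/92.7 = 8.7%.

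**Chance of a positive conclusion (%).**

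| True TPF/FPF, direction | Limits | q = 0 | 5% | 10% | 20% | 30% |
|---|---|---|---|---|---|---|
| 90/20, toward | 90% | 3.1 | 4.9 | 6.9 | 13.3 | 25.0 |
| 90/20, toward | 80% | 6.4 | 9.7 | 14.3 | 26.0 | 40.9 |
| 70/20, toward | 90% | 0.1 | 0.2 | 0.3 | 1.0 | 2.7 |
| 70/20, toward | 80% | 0.5 | 0.9 | 1.5 | 3.9 | 8.0 |
| 70/6, toward | 90% | 3.0 | 3.0 | 3.1 | 3.5 | 4.1 |
| 70/6, toward | 80% | 7.6 | 7.7 | 7.8 | 8.4 | 9.5 |
| 90/6, away | 90% | 81.8 | 77.4 | 67.8 | 43.7 | 19.7 |
| 90/6, away | 80% | 92.4 | 88.1 | 81.9 | 63.1 | 37.8 |

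Only the 90/20 corner passes 0.1. It does so at about 16% drift with 90% limits (10.2%) and about 6% with 80% limits (10.6%). At 2% drift the 90/20 chance goes from 3.12% to 3.77% (90% limits) or from 6.37% to 7.58% (80% limits).

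**The case against.** The design already does much of the work. Targeting in the 12-core biopsy is barred in two sections, with reasons. The upgrade criteria in 5.3.4.2 are fixed limits. Source labels keep targeted cores from being pooled into the reference result by accident, and 5.3.4.2 and 5.3.4.3 need those labels because their criteria differ. What remains is the chance that staff depart from a written instruction or shade a borderline read, and every figure above rests on an assumed rate. At the plan's joint null, even 30% drift leaves the chance of a positive conclusion below 0.1. All of this stands, and it limits the point to a recommended change.

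Some later repair is possible. "All specimens will be formalin fixed and paraffin embedded as per usual clinical care", so a masked re-read could be done if material is kept. "Each core will be individually labeled with laterally and anatomic site within the prostate", and the optional spatial tracking in 5.3.3 would help to audit placement. But the plan schedules neither check, and core placement cannot be redone.

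A fixed biopsy order also has a possible cost. Section 5.2 prefers to delay the MRI because of post-biopsy hemorrhage, so taking 12 fresh cores first might affect an MRI-guided targeted procedure. Section 5.3.3 leaves that procedure to local practice. This is a fair reason not to prescribe the order here.

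A reader might infer that the reference standard is biased, or that the MRI's accuracy will be overstated. The documents support neither: they show an opening, with no evidence of influence and no direction.

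**Conclusion.** The point holds as a gap in masking and in the record of biopsy order. Followed as written, the plan lets the reader of the reference standard infer the index-test result in MRI-positive men, and it cannot show that the 12 cores were taken without guidance from the MRI. The size is conditional on drift. It is about a percentage point or less at 2% drift. At 10% drift away from the MRI, the chance of success at the promising values falls by 14.0 points (90% limits) or 10.5 points (80% limits). Drift toward the MRI breaches the 0.1 level only where TPF is good and FPF is unacceptable. The 70/20 and 70/6 corners stay below 0.1 up to 30% drift under either limit, so a general inflation of the error rate should not be inferred. These results assume exact limits, a 30/90 split and one drift rate for all upgrade criteria. The change is worth making because the masked read uses a review that is already planned.

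**What to change.** **Section 5.3.4.** Have the already planned pathology review read the 12-core set of every man in groups 1 and 2 under coded numbers, without the MRI category and before any targeted cores are seen. Lock that result for the primary endpoint. Coding both groups keeps the code itself from revealing the MRI. Keep the source labels for 5.3.4.2 and 5.3.4.3.

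**Sections 5.3.2 and 5.3.3.** Have each site state, and record on the case report form, the order of the two biopsies and whether MRI targets were displayed when the 12 cores were taken. Leave the choice of order to the investigators.

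**Section 11.4.** Where masked reading is not possible, record this, and report TPF and FPF with and without all men from that site, in both MRI groups. Dropping only MRI-positive men would itself lower both measures. For example, removing 8 of the 32 reclassified men in the alternative table in proportion gives TPF 20.25/23.25 = 87.1% and FPF 3.75/88.75 = 4.2%, against 90% and 5.6%.

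**Cost.** A few protocol sentences, two form fields, coded numbers and a staged read at each site; no extra reader, biopsy or patient. The documents do not say whether the DF/HCC review in the Study Calendar is separate from the treating-center read in 5.3.4. If they are the same, the staging falls on that read.

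**Residual limit to state.** An operator who has read the clinical MRI report is still not masked.
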